## **6.3 Change in Qmax**

Change from baseline to 3 months in Qmax, a uroflow measurement. Calculations will be performed with and without patients with a catheter at the time of assessment. The “with” analysis will assume a Qmax of 0 for any patient with a urinary catheter in place at the time testing. Mean and confidence intervals will be calculated using a t test (two-tailed, alpha=.05) against a null hypothesis of no change and a historical semi-quantitative comparison will be made with WATER study data or other studies.

## **6.4 Change in PVR**

Change from baseline to 3 months in PVR. Calculations will be similar to those for Qmax, i.e., calculations with and without patients who are catheterized. For a patient with a urinary catheter in place at the time testing, the PVR value will be assessed as not applicable. Mean and confidence intervals will be calculated using a t test (two-tailed, alpha=.05) against a null hypothesis of no change and a similar semi-quantitative comparison will be made to WATER and/or other studies.

## **6.5 Change in PSA**

Change from baseline to 6 months in PSA. Mean and confidence intervals will be calculated using a t test (two-tailed, alpha=.05) against a null hypothesis of no change.

## **6.6 Change in MSHQ-EjD**

Mean change from baseline in MSHQ-EjD score at 3 months. Preservation of ejaculatory function is defined as a change non-inferior to -4 points. (Note that there is no published minimally clinically important difference for MSHQ-EjD.) A t test with 95% confidence intervals will be used to evaluate this hypothesis. If non-inferiority is concluded, a secondary test will calculate whether the change score represents statistical superiority.

## **6.7 Change in IIEF-5**

Mean change from baseline in IIEF-5 (aka SHIM, part of IIEF-15) at 3 months. Preservation of erectile function, meaning a change score non-inferior to -6 points. An approach similar to that listed for MSHQ-EjD will be used.

## **6.8 Reintervention Rate**

Re-intervention rate at 3 months. Re-intervention is defined as the need for additional prostate tissue resection following the index procedure. An exact binomial confidence interval (binom.test) will be calculated. No statistical hypothesis is proposed.

## **6.9 Urinary Catheter Discontinuation**

The proportion of participants who were using a urinary catheter at any time 45 days prior to enrollment who are not using a catheter any time 45 days prior to the 3-month visit will be assessed. No statistical hypothesis is proposed.

## **7 ADDITIONAL ENDPOINT ASSESSMENTS**

Additional exploratory statistical analysis will be done using standard statistical methods. Analyses of interest are:

1. Proportion/rate of all Clavien-Dindo classifications at month 3.
2. Changes in the following ratings across all time points: IPSS, IPSS-QOL, Incontinence Severity Index (ISI), IIEF-15, MSHQ-EjD, pelvic pain intensity score, dysuria frequency and intensity score, and uroflow measures. For this and other repeated assessments, repeated measures analysis of variance may be used to calculate change from baseline. Semi-quantitative comparisons will be made to results from WATER.
3. Relationship between baseline IPSS and IPSS change scores.
4. Duration of bladder catheterization.
5. Whether discharged home with a bladder catheter.
6. Change in hemoglobin from preoperative to postoperative. Additional analysis will be performed to see if prostate size, anesthesia type, number of Aquablation passes, and intravesical median lobes were predictors of bleeding loss.
7. Reoperation rate at 1 year for lack of efficacy. (This endpoint excludes reoperation for complications.)
8. Change in proportion of subjects using BPH medications (e.g., alpha blockers, alpha-reductase inhibitors).
9. Prostate size reduction from baseline to 3 months as measured TRUS. A t test will be used for the comparison.
10. Relationship between prostate size and procedure or resection times. Linear or other models will be used to explore relationships.
11. Proportion of subjects with device- or procedure-related adverse event.
12. Proportion of subjects in whom re-catheterization was needed between discharge after the index procedure and month 3. Re-catheterization is defined as the need to place a urinary catheter in the bladder for symptoms related to BPH (primarily inability to urinate). This excludes re-catheterization for study purposes or for purposes unrelated to LUTS.
13. Amount of irrigation fluid used intraoperatively (liters). A t test or Wilcoxon's test will be used to compare to values from WATER.

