## 2.9 Study Duration

Each subject is followed postoperatively through 60 months. Total study duration from first subject enrolled to last subject completing the 60 months follow-up visit is expected to take approximately six years.

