## 2.11 Sample Size

One hundred and one (101) participants who received study treatment under protocol rev. A.

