**Incontinence Severity Index:** ISI is a validated means of assessing incontinence and will assist in isolating *de novo* incontinence rather than pre-existing incontinence secondary to Bladder Outlet Obstruction (BOO). This questionnaire will be completed at baseline, 1 month, 3 months, 6 months and 12 months follow-up visit.

**International Prostate Symptom Score (IPSS):** IPSS is a validated measure of urinary dysfunction due to BPH. This questionnaire will be completed at baseline, 1 month, 3 months, 6 months, 12 months, 24 months, 36 months, 48 months, and 60 months visit.

**Pain Severity Assessment (NRS) and Dysuria Score:** NRS and Dysuria Scores are a method of measuring post-operative pain and pain on micturition. This questionnaire will be completed at baseline, 1 month, 3 months and 6 months follow-up visit.

**International Index of Erectile Function Questionnaire (IIEF-15):** IIEF-15 is a validated, fifteen-item questionnaire designed to diagnose the presence and severity of erectile dysfunction. This questionnaire will be completed at baseline, 1 month, 3 months, 6 months, and 12 months follow-up visit. IIEF-5 is a subset of IIEF-15 that has also been validated for the measurement of erectile function.

**Male Sexual Health Questionnaire to assess Ejaculatory Dysfunction (MSHQ-EjD):** MSHQ-EjD is a validated, four-item questionnaire that assesses ejaculatory function and related distress or bother. This questionnaire will be completed at baseline, 1 month, 3 months, 6 months, and 12 months follow-up visit.

**Quality of Recovery.** This is a validated visual analog scale rating of quality of recovery from surgery. The scale extends from “poor recovery” to “excellent recovery.”

**Transrectal ultrasound (TRUS):** TRUS will be performed to assess eligibility for prostate volume, length, transverse width, anterior/posterior width, and general condition of the prostate. Presence of a middle or intravesical lobe should be documented by sagittal images. TRUS will be conducted at baseline, treatment, and 3 months follow-up visit.

**Concomitant Medications:** The following will be recorded on a rolling log: BPH medication, post-operative pain medication, all AE related medications up to the 12 months visit, and all urological SAE and urological AE related medications for the 24 months, 36 months, 48 months, and 60 months visits.

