## **4 STATISTICAL ANALYSIS**

### ***4.1 General Approach***

**Continuous Outcomes.** Continuous outcomes will be summarized with mean, standard deviation and other relevant statistically summaries. When not normally distributed, medians and quantiles will be reported. A confidence interval approach may be used, if appropriate, to compare outcomes with historical information. Repeated measures analysis of variance may be used for outcomes assessed multiple times over the course of follow-up.

**Binary Outcomes.** Binary and ordinal outcomes will be tabulated. Rates will be expressed as a percentage taking into account denominators as listed above. If required, confidence intervals for proportions will be calculated using the exact binomial distribution. A confidence interval approach may be used to compare outcomes with historical information. Comparisons of proportions will be done with chi-squared or Fisher's exact test. Multivariate analysis may also be performed.

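### The only model named for ratings over repeated visits is an optional repeated measures ANOVA with no rule for missed visits; a pre-specified mixed model would serve IPSS and uroflow to 60 months better at little cost.

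*SAP*

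**What the plan says.** SAP section 7 opens with "Additional exploratory statistical analysis will be done using standard statistical methods". Item 2 lists IPSS, its quality-of-life score, the incontinence index, IIEF-15, MSHQ-EjD, pain, dysuria and uroflow at all time points, and adds that "repeated measures analysis of variance may be used to calculate change from baseline". Protocol 4.1 has the matching sentence: "Repeated measures analysis of variance may be used for outcomes assessed multiple times over the course of follow-up". The same section commits to descriptive summaries of continuous outcomes; only the ANOVA is optional.

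Follow-up is long: "Each subject is followed postoperatively through 60 months". The instruments differ in how far they go:

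- IPSS has eight post-treatment visits, the last at 60 months ("12 months, 24 months, 36 months, 48 months, and 60 months visit"). Uroflow has the same visits.
- For the incontinence index, "This questionnaire will be completed at baseline, 1 month, 3 months, 6 months and 12 months follow-up visit". IIEF-15 and MSHQ-EjD also stop at 12 months.
- For pain and dysuria, "This questionnaire will be completed at baseline, 1 month, 3 months and 6 months follow-up visit".

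The sample is "One hundred and one (101) participants who received study treatment under protocol rev. A". On missing data, SAP 5.1 gives imputation rules for the 3-month IPSS change only, and SAP 4.2 rules out imputation in the per-protocol cohort. Under Protocol 2.22 a man is lost to follow-up only after missing two visits in a row, so a man still in the study can have gaps. SAP 9 plans mixed models, but only for differences between sites.

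**The concern.** Repeated measures ANOVA has two common forms, and the plan does not choose between them. The classical (wide-format) form needs a complete row per man, so one missed visit out of eight removes all his data. The long-format form with a pooled within-subject error keeps him, but its standard errors rest on equal correlations between all pairs of occasions. Two analysts following this plan could therefore report different 60-month results.

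What is at stake is the long-term IPSS and uroflow description, which item 2 also sets beside WATER. Deleting incomplete men wastes observed data. If men with less improvement leave sooner, the men who remain look better than the treated group.

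**Working it through.** **The plan's own figure.** None is stated for this analysis. The nearest is the 99% power for the 3-month IPSS test: (16 − 11)/(7.5/√90) = 6.32; 6.32 − 1.96 = 4.36; power above 99.9%. That is in line with the stated 99%, and it does not depend on the repeated-measures method.

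**Inputs.** From the documents: 101 men, and baseline plus 8 visits for IPSS. Assumed, because the documents give only 10% loss for the 3-month analysis: total drop-out d by 60 months, the chance m of missing a single visit, the link between drop-out and outcome, and the variances and correlations used in the simulations.

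**Men with every visit.** Expected number = 101 × (1 − d) × (1 − m)^8.

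| d | m = 0 | m = 2% | m = 5% |
|---|---|---|---|
| 10% | 91 | 77 | 60 |
| 20% | 81 | 69 | 54 |
| 30% | 71 | 60 | 47 |

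Instruments with fewer visits suffer less. At 5% missing per visit, 0.95^8 = 66% of men are complete over eight visits, 0.95^4 = 81% over four and 0.95^3 = 86% over three.

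**Precision.** Simulation of 500 trials per setting: IPSS SD 6, true 60-month improvement 15.3, 3% of visits missed singly, drop-out unrelated to outcome (MCAR). The mixed model is likelihood-based with unstructured covariance over the nine occasions.

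| Drop-out | Men kept by classical ANOVA | SE classical | SE mixed model | Ratio |
|---|---|---|---|---|
| 10% | 72 | 0.87 | 0.77 | 1.13 |
| 20% | 64 | 0.96 | 0.77 | 1.25 |
| 30% | 55 | 1.02 | 0.80 | 1.28 |
| 40% | 48 | 1.09 | 0.82 | 1.33 |

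Bias was negligible for both methods here. The ratio depends on the missingness pattern. In a separate run (SD 7.5, 5% missing per visit, true covariance supplied to the model) it was about 1.10 with permanent drop-out only and equal correlation 0.6. It was about 1.01 if the correlation decays, and about 1.20 if all missed visits are isolated.

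**Bias.** Same simulation as the table above, with the odds of drop-out multiplied by 1.65 (weaker link) or 2.7 (strong link) per SD of worse IPSS. Under MAR drop-out depends on the last observed score; under MNAR it depends on the unseen one. Entries are points of overstated 60-month improvement, classical / mixed model; Monte Carlo error is about 0.04.

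| Drop-out | MAR, weaker | MAR, strong | MNAR, weaker | MNAR, strong |
|---|---|---|---|---|
| 10% | 0.08 / −0.06 | 0.28 / 0.06 | 0.14 / 0.06 | 0.37 / 0.21 |
| 20% | 0.22 / −0.02 | 0.48 / 0.03 | 0.28 / 0.12 | 0.55 / 0.21 |
| 30% | 0.35 / 0.02 | 0.69 / −0.04 | 0.45 / 0.16 | 0.88 / 0.36 |
| 40% | 0.50 / −0.01 | 1.00 / 0.01 | 0.62 / 0.25 | 1.14 / 0.47 |

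A second simulation (true change 16, SD 7.5, about 5% MAR drop-out per visit, so 1 − 0.95^8 = 34% lost) put the completer mean at 16.6 to 17.2 with equal correlation 0.6, and at 16.2 to 16.4 with decaying correlation. The order of size is the same, and the correlation assumption matters.

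**Equal correlations in the long-format form.** SAP 5.1 reports that 3-month change in WATER depended strongly on baseline because most scores fall close to the best possible. That suggests a weak correlation between baseline and follow-up. Assume 0.1 between baseline and each follow-up, 0.6 between follow-ups, equal variances σ² and complete data:

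- Mean of the 36 pairwise correlations: (8 × 0.1 + 28 × 0.6)/36 = 0.489.
- Pooled-error variance of a change, per man: 2 × (1 − 0.489) = 1.022σ².
- True variance: 2 × (1 − 0.1) = 1.8σ².
- SE ratio: √(1.8/1.022) = 1.33. Coverage of a nominal 95% interval: 2Φ(1.96/1.33) − 1 ≈ 86%.

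With 0.2 and 0.5 the mean correlation is 0.433, the ratio √(1.6/1.133) = 1.19 and coverage 90%.

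**The case against.** A reader might infer that the plan commits to analysing only men with every visit. It does not. The ANOVA is optional, no routine is named, and long-format aov in R, the SAP's software, keeps men with gaps. In the first simulation its bias under MAR stayed within about 0.1 point, and under MNAR it was no worse than the mixed model's. That stands. What it leaves open is which form would be used, and the equal-correlation assumption behind its intervals.

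The committed output is descriptive and need not drop anyone for an unrelated missed visit. That also stands, but simple available-case means carry the same selection bias: 0.49 and 1.02 points at 20% and 40% drop-out under MAR with a strong link, against 0.48 and 1.00 for complete cases.

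A reader might also take 1/√0.663 = 1.23 (or 1/√0.430 = 1.52 at 10% missing per visit) as the precision lost. Those factors compare completers with no missing data at all. Much of that loss is drop-out itself, which no model recovers.

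Finally, the section is exploratory, with no alpha, and Protocol 2.8 states the objective at 3 months. Neither document says that durability is the purpose of the 60-month follow-up. This limits the importance of the point but does not supply a rule for missed visits.

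**Conclusion.** The point holds as a cheap improvement. The one model named for repeated ratings is either wasteful of incomplete men or dependent on equal correlations, and the plan is silent on missed visits. Among the listed ratings, only IPSS (taking its quality-of-life item to be collected with it) and uroflow are affected to 60 months.

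For those, the classical form costs about 13 to 33% in standard error against a mixed model at 10 to 40% random drop-out, and less if drop-out is permanent and correlations decay. If poorer results lead men to leave, it overstates 60-month improvement by about 0.1 to 1.1 IPSS points against a true 15.3. All of this rests on assumed drop-out and correlations; with drop-out unrelated to outcome there is no bias.

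A reader might conclude that a mixed model cures the problem outright. It removes the bias only under MAR. In the strong MNAR settings at 20 to 40% drop-out, about 40% of it remained (0.21 of 0.55; 0.47 of 1.14). The primary 3-month test is unaffected.

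**What to change.** Replace the ANOVA sentences in SAP section 7 item 2 and Protocol 4.1 with wording such as: Outcomes at multiple visits will be analysed with a likelihood-based linear mixed model for repeated measures using all observed visits, with visit as a factor, baseline value as covariate and unstructured covariance; the order of fallback structures and the degrees-of-freedom method are fixed in advance. The analysis assumes data missing at random. The number observed and the change with 95% CI are reported at each visit. For 60-month IPSS, a sensitivity analysis allows for data missing not at random.

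The cost is small: wording in two documents, a little more analysis work and no new data. There is a modest technical downside. With baseline as covariate, the unstructured 8 × 8 covariance has 8 × 9/2 = 36 parameters from 101 men, so the fallback may be needed and must be named.

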## **8 SUBGROUP ANALYSES**

Subgroup analyses of primary safety and effectiveness endpoints, as well as selected secondary endpoints, will be performed for the following subgroups:

- baseline IPSS scores of <20 vs.  $\geq$ 20
- baseline prostate size of <100g vs.  $\geq$ 100g
- Age <65 vs.  $\geq$ 65 years at baseline

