## 2.12 Study Population

Men with lower urinary tract symptoms due to BPH resulting from a large prostate size (80-150 mL). To participate, a patient must meet all inclusion criteria and none of the exclusion criteria listed in **Table 1**.

*Table 1 Study Eligibility Criteria*

| Inclusion Criteria   | Exclusion Criteria   |
|--|--|
| 
 
a) Male age 45-80 years
 
b) Subject has diagnosis of lower urinary tract symptoms due to benign prostatic enlargement causing bladder outlet obstruction
 
c) Subject has an IPSS score greater than or equal to 12
 
d) Maximum urinary flow rate (Qmax) less than 15mL/s
 
e) Serum creatinine < 2 mg/dL within 30 days of surgery
 
f) History of inadequate or failed response, contraindication, or refusal to medical therapy
 
g) Prostate size <math>\geq</math> 80 mL and <math>\leq</math> 150 mL as measured by TRUS
 
h) Patient is mentally capable and willing to sign a study-specific informed consent form
 
 | 
 
a) BMI <math>\geq</math> 42
 
b) Patients unable to stop anticoagulants, antiplatelet agents, or non-steroidal anti-inflammatory agents (NSAIDs, including aspirin greater or equal to 100mg) prior to treatment per standard of care
 
c) History of gross haematuria
 
d) Participants using systemic immune-suppressants including corticosteroids (except inhalants); unable to withhold non-steroidal anti-inflammatory agents (NSAIDs, including aspirin) prior to treatment per standard of care except for low dose aspirin (e.g. less than or equal to 100mg)
 
e) Known coagulopathy or platelet disorder
 
f) Contraindication to both general and spinal anesthesia
 
g) Any severe illness that would prevent complete study participation or confound study results
 
h) History of prostate cancer or current/suspected bladder cancer. Prostate cancer should be ruled out before participation to the satisfaction of the investigator if PSA is above acceptable thresholds
 
i) History of actively treated bladder cancer within the past two (2) years
 
j) Diagnosis of polyneuropathy
 
k) Clinically significant bladder calculus or bladder diverticulum (e.g., pouch size <math>>20\%</math> of full bladder size)
 
l) Active infection, including urinary tract infection or prostatitis
 
 |

|  |   |
|--|---|

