### ***4.2 Primary Endpoint Calculation and Sample Size Determination***

Prior studies have shown that IPSS scores are reduced by approximately 16 points after Aquablation, values similar to those observed after TURP. In patients with moderate-to-severe BPH, the mean change in IPSS score representing slight improvement is approximately 5 points. Therefore, showing a mean reduction in IPSS scores that statistically exceeds  $16-5 = 11$  points will be interpreted as study success. The study's primary endpoint hypothesis is a one-way statistical test (alpha=.025 for interpretation):

$$\begin{aligned} H_0: \text{Mean(IPSS change score at 3 months)} &\leq 11 \\ H_a: \text{Mean(IPSS change score at 3 months)} &> 11 \end{aligned}$$

With 100 patients and assuming 10% subjects lost to follow, 90 evaluable subjects with an underlying change of 16 points and a change score SD of 7.5 points yields a 99% power to detect an improvement of more than 11 points.

The WATER study (IDE#G150089) used an assumption that a TURP rate for the same safety definition provided in this protocol would be 65% for a range of prostate sizes 30-80mL. The same safety target will be used for this protocol treating large prostates of 80-150mL. The assumed true rate for the Aquablation patients will be 50% (10% greater than WATER in order to account for treating larger prostates). The study's primary endpoint hypothesis is a one-way statistical test (alpha=.025 for interpretation):

$$\begin{aligned} H_0: \text{Mean (safety rate at 3 months)} &\geq 65\% \\ H_a: \text{Mean (safety rate at 3 months)} &< 65\% \end{aligned}$$

The primary safety endpoint with 90 evaluable subjects has an 80% power to detect a safety rate of less than 65%.

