## **5 STUDY ENDPOINTS**

### **5.1 Primary Effectiveness Endpoint**

The primary effectiveness endpoint is the IPSS change score from baseline to 3 months. IPSS is an accepted and commonly used measure for symptom severity in BPH. IPSS varies from 0 (no symptoms) to 35 (maximal symptoms). The mean 3-month IPSS change score (abbreviated dIPSS3) in WATER was 16 points (SD=7 points). WATER used a non-inferiority margin of 5 points; 5 points represents the minimum change for men with moderate-to-severe BPH that is detectable. The current study's goal is therefore to show that the IPSS change score statistically exceeds 16-5 = 11 points. The study's hypotheses are therefore:

$$\begin{aligned} H_0: \text{dIPSS}_3 &\leq 11 \\ H_a: \text{dIPSS}_3 &> 11 \end{aligned}$$

A one-way t test with the mITT cohort will be used for the calculation. With 100 patients and assuming 10% subjects lost to follow, 90 evaluable subjects with an underlying change of 16 points and a change score SD of 7.5 points yields a 99% power to detect an improvement of more than 11 points.

A secondary goal is to show similarity of change scores between WATER II and WATER. Data from WATER and WATER II will be combined. Regression analyses controlling for baseline IPSS score (a strong predictor of change scores) will calculate differences in change scores between WATER and WATER II subjects. WATER II will be determined to have similar dIPSS3 scores if the 95% confidence limits for the difference between WATER and WATER II Aquablation subjects exceeds -5 points. The study is not necessarily powered for this comparison.

Missing data for dIPSS3 will be imputed using the following rules:

- Predicted value from baseline IPSS: In WATER, dIPSS3 was strongly and statistically significantly related to baseline IPSS (Figure 1). This finding is not surprising for maximally effective procedures that reduce scores to close to maximal (i.e., a ceiling effect). A linear regression model using WATER II available data will be used to predict missing change scores.
- Low value: A change score of 0 points
- High value: a change of 5 less than the maximal possible improvement, which represents change scores from WATER (see also Figure 1)

[figure not shown]

Figure 1. Relationship between baseline IPSS and 3-month change score in WATER. Blue = Aquablation, red = TURP.

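### SAP 8 pre-specifies prostate size and age against the primary endpoints only as two-group splits; exploratory continuous terms would use the same data better if the trends are roughly linear

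*SAP*

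**What the plan says.** SAP 8 states: "Subgroup analyses of primary safety and effectiveness endpoints, as well as selected secondary endpoints, will be performed for the following subgroups". The list then gives three two-group splits: baseline IPSS at 20, prostate size ("baseline prostate size of <100g vs" 100 g and above) and age at 65 years. It names no contrast, interaction test, trend test or continuous model.

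The eligible ranges are wide relative to these cuts. Protocol 2.12 describes the population's symptoms as "resulting from a large prostate size (80-150 mL") and its first inclusion criterion is "Male age 45-80 years". The SAP writes the size range in grams and the protocol in mL; they are treated as the same scale here.

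Size is handled more fully for other outcomes. SAP 7 item 10 plans "Relationship between prostate size and procedure or resection times", with linear or other models, and item 6 examines size as a predictor of blood loss. Item 3 relates baseline IPSS to IPSS change. No item does the same for size or age against IPSS change or the primary safety event.

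Other sections leave room for more modelling without committing to it:

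- Protocol 3.4 and 4.1 permit additional or multivariate analysis, with no covariate named.
- SAP 9 allows covariate models to explain differences between sites. Its examples for IPSS change include neither prostate size nor age, and its safety regression applies only if sites prove not poolable.
- SAP 5.1 plans a pooled regression of WATER and WATER II IPSS change, which is a contrast between trials.

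**The concern.** The plan itself treats gland size as relevant to outcome. SAP 1 names larger prostates as a major difference from WATER. Protocol 4.2 sets the assumed safety event rate at 50%, which it describes as 10% above WATER to allow for larger glands. It is natural to ask whether benefit falls or complications rise between 80 and 150 mL.

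A split at 100 g answers that weakly when the relation is gradual. Men at 101 g and 149 g count as alike, while men at 99 g and 101 g count as different. The estimate of a gradient is then less precise than the data allow. The same reasoning applies to age. What is at stake is the precision of an exploratory reading, not the primary conclusions.

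**Working it through.** **Inputs from the documents.** SAP 5.1: "With 100 patients and assuming 10% subjects lost to follow", then "90 evaluable subjects with an underlying change of 16 points and a change score SD of 7.5 points yields a 99% power". The success bound is 11 points, so the difference is 16 − 11 = 5. Protocol 4.2 gives one-sided alpha 0.025 for the primary tests and an assumed safety rate of 50%. Size range 80-150 with a cut at 100; age range 45-80 with a cut at 65. Protocol 2.2 reports age 67.7 ± 6.7 years in the two earlier trials.

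**Assumptions.** The distribution of prostate size in this trial is not given, so a range of shapes is tried. Two-sided 0.05 is assumed for subgroup contrasts because SAP 8 states no level. The trend is taken as linear unless stated otherwise.

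**Step 1: the plan's own figure.** Noncentrality = 5 / (7.5/√90) = 6.32. The one-sample t test at one-sided 0.025 then has power 99.999%, consistent with the stated 99%. The n and SD can therefore be carried forward. The documents give no figure for the subgroup analyses.

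**Step 2: information lost on a linear size trend.** Loss = 1 − r², where r is the correlation between size and the indicator of size ≥ 100. For a uniform distribution:

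- share at or above 100: p = 50/70 = 0.714
- group means 125 and 90, a gap of 35
- variance = 70²/12 = 408.3
- r² = p(1 − p) × 35² / 408.3 = 0.204 × 1225 / 408.3 = 0.612, so the loss is 39%

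The same formula, integrated numerically over other shapes truncated to 80-150, gives:

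| Assumed size distribution | Share ≥ 100 | Loss |
|---|---|---|
| Exponential from 80, scale 10-30 | 14-46% | 31-37% |
| Normal, mode 80-100, SD 15-30 | 18-65% | 32-39% |
| Uniform | 71% | 39% |
| Normal, mode 105-110, SD 15-30 | 66-76% | 40-48% |
| Normal, mode 115, SD 15-30 | 75-85% | 44-57% |
| Normal, mode 120, SD 15-30 | 79-91% | 46-67% |

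Setting aside the last row, which puts most men far above the cut, the range is about 30-55%.

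**Step 3: age split at 65 within 45-80.** Uniform: 27%. Truncated normals with mean 62-70 and SD 6-8: 34-45%. With the earlier trials' 67.7 and 6.7: 36%.

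**Step 4: what this means for IPSS.** Take 90 men, SD 7.5 and uniform size (SD of size √408.3 = 20.2).

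- Continuous term, gradient over 70 mL detectable with 80% power: (1.960 + 0.842) × 7.5 × 70 / (√90 × 20.2) ≈ 7.7 points.
- Split, with 25.7 and 64.3 men: the detectable difference between groups is 2.802 × 7.5 × √(1/25.7 + 1/64.3) ≈ 4.9 points. The group means lie 35 mL apart, so this corresponds to 4.9 × 70/35 ≈ 9.8 points over the range.

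The 95% CI half-widths for the same gradient scale by 1.960/2.802: about 5.4 points with the continuous term and 6.9 with the split.

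Expressed as power, a trend test that would have 80% with the continuous term has Φ(√(1 − loss) × 2.802 − 1.960): 63% at a loss of one third, 59% at 39%, and 55% at 45%.

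**Step 5: safety.** With the event rate near 50% (SD 0.5), the split has 80% power only for a difference of 2.802 × 0.5 × √(1/25.7 + 1/64.3) ≈ 33 percentage points between the groups.

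**Step 6: if the trend is not linear.** If the effect is a step exactly at 100, the split loses nothing. The linear term then loses the same 1 − r²: 39% for uniform size, or 31% for an exponential with scale 20.

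**The case against.** The strongest defence is that SAP 8 contains no error. The cuts are fixed in advance, which prevents choosing a favourable one later, and two-group tables are conventional and easy to read. The purpose in SAP 1 is safety and efficacy in the target population as a whole. The primary tests compare the full cohort with fixed bounds, and no objective, hypothesis or power statement concerns a gradient within 80-150 mL. A reader might infer that such a gradient is the trial's central internal question; the documents do not say so.

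The plan also looks at size elsewhere: as a predictor of blood loss, against procedure time, and through the WATER comparison, since Protocol 4.2 gives WATER's range as 30-80 mL. This stands as context, but none of it models a primary endpoint within this trial's size range. The permissions in Protocol 3.4 and 4.1 and SAP 9 are optional or conditional, and permission is not pre-specification.

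The linearity objection also stands. A linear term is not better for every shape (Step 6), so it needs a check of form. Neither document gives a reason to expect a step at 100 g.

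A reader might also take the loss as a fixed third of the data, or as men thrown away. Neither is supported. Every man is analysed, the loss concerns the precision of one slope, and its size depends on an unreported distribution and a linear trend.

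**Conclusion.** The point holds as a low-cost improvement to an exploratory section. SAP 8 commits only to two-group splits of size and age against the primary endpoints, and no other section commits to more.

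If the trends are linear, the loss of information is roughly 30-55% for size (39% if uniform) and about 27-45% for age (36% with the earlier trials' mean and SD). In the uniform case the detectable IPSS gradient is 7.7 points with a continuous term against 9.8 with the split. Both exceed the 5 points that SAP 5.1 treats as the smallest detectable change, so the continuous term sharpens the estimate without making the analysis well powered.

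It would be wrong to conclude that the primary results are weakened: the primary tests, their alpha and their power do not change. The case for age is weaker than for size, because the documents give no stated reason to expect an age effect.

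**What to change.** In SAP 8, add as exploratory analyses:

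- linear regression of 3-month IPSS change on continuous prostate volume and age, with baseline IPSS in the model;
- logistic regression of the primary safety event on continuous prostate volume and age;
- for each, 95% CIs, predicted values across 80-150 mL (for example at 80, 115 and 150), and a simple check of linearity such as a quadratic term or a smoothed plot.

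Keep the pre-specified 100 g and 65-year tables for display.

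The cost is a few lines of SAP text and two more exploratory models, with some reliance on an approximately linear form. No new data are needed, because age, baseline TRUS volume, IPSS and adverse events are already in the schedule of assessments. At the assumed 50% rate, 90 men give about 45 safety events, enough for a logistic model with two terms.
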